5.5 PATIENT REGISTRATION

After the patient has signed the ICF and all eligibility criteria have been met, the patient will be included into the trial. A patient number will be provided at the time of registration. This number should be used in all future documentation and correspondence referring to this patient. Investigators are under no circumstances allowed to treat any patient before appropriate reception of the patient registration number.

5.6 PATIENT RANDOMIZATION

Not applicable.

5.7 EVALUATIONS DURING TREATMENT

The following assessments will be done while the patient is on treatment ([Table 4](#)).

Table 4. Evaluations during treatment.

	ASSESSMENT	TIME
1. Clinical examination	
 Complete physical examination, including weight and calculation of BSA. Dose will be adjusted if BSA change is $\geq 10\%$ (higher or lower) of the previous value. 	Day 1 of each cycle (always prior to PM01183 infusion).*
	
 Performance status (ECOG PS). Vital signs: heart rate, blood pressure and body temperature. 	Day 1 of each cycle (always prior to PM01183 infusion).*
	
 Concomitant therapies. 	Throughout the “on treatment” period.**
2. Laboratory tests	
 Coagulation panel: PT/INR and PTT. 	Day 1 of each cycle (always prior to PM01183 infusion).*
	
 Hematology: Hemoglobin, platelet counts, and differential WBC counts (including neutrophils, monocytes and lymphocytes). Biochemistry A: Serum electrolytes (Na⁺, K⁺, Cl⁻), AST, ALT, AP, GGT, total bilirubin (direct bilirubin to be measured only if total bilirubin is $>1.5 \times \text{ULN}$), LDH, creatinine, glucose, and CPK. 	
Cycle 1 and 2: Day 1, 8 and 15 (always prior to PM01183 infusion).*
 
Two blood samples (24 hours and 72 hours after the end of PM01183 infusion) will be collected at the same time than PK samples #6 and #7 in Cycle 1 for monocyte count.
 
Further cycles: Day 1 of each cycle (always prior to PM01183 infusion).*
 
From Cycle 2 onwards, Hematology and Biochemistry A tests on Days 8 and 15 are to be performed only in patients who present biochemical grade ≥ 3 or hematological grade > 4 treatment-related toxicities, or who required dose adjustments due to hematological or biochemical abnormalities in the preceding cycle.
 
Any patient presenting a grade ≥ 3 treatment-related AE should have all relevant tests re-assessed at least every 48-72 hours until recovery to grade ≤ 2.
 
Any patient having febrile neutropenia of

	ASSESSMENT	TIME
		any grade, grade 4 neutropenia, and/or grade 4 thrombocytopenia, should have relevant tests repeated daily until recovery to grade ≤ 3 and up to the next day after fever resolution, if applicable.
	
♦ Biochemistry B: Albumin, total proteins, total calcium and Mg⁺⁺. In patients with germ cell tumors, β-hCG and AFP only in those patients with elevated values at baseline.
	
Albumin: Day 1 of each cycle (always prior to PM01183 infusion). *
 
Total proteins, total calcium and Mg⁺⁺ will be measured only in those patients with abnormal baseline values.
 
Any patient presenting a grade ≥ 3 treatment-related AE should have all relevant tests re-assessed at least every 48-72 hours until recovery to grade ≤ 2.

3. Pharmacokinetics	
♦ Cycle 1: Eight blood samples (before PM01183 infusion start, 5 min before end of PM01183 infusion and 30 min, 1 hour, 3 hours, 24 hours, 72 hours and 168 hours after the end of PM01183 infusion) will be collected for pharmacokinetic analyses (see details in Section 7.2.1).
 
♦ Cycle 2: Six blood samples (before PM01183 infusion start, 5 min before end of PM01183 infusion and 30 min, 1 hour, 3 hours and 168 hours after the end of PM01183 infusion) will be collected for pharmacokinetic analyses (see details in Section 7.2.1).
	Cycle 1 and Cycle 2.
4. AAGP	One blood sample per cycle.	On Day 1 of Cycle 1 and Cycle 2 (always prior to PM01183 infusion).
5. Pharmacogenetics (only if written informed consent given)	One blood sample.	At any time during the study, but preferably just before treatment start in Cycle 1.
6. Pregnancy test (if women of childbearing potential)	β -hCG (urine or serum). In patients of childbearing potential (except germ cell tumor patients), if β -hCG levels are elevated, pregnancy must be clinically discarded by an additional test (i.e., ultrasound) before any other study procedure. Pregnancy during treatment or within three months from the patient's last PM01183 administration is considered an immediately reportable event.	Day 1 of each cycle (always prior to PM01183 infusion).*
7. ECG	Cardiac rhythm will be identified in ECG intervals of at least 30 seconds of duration, PR interval, QT interval (raw), heart rate and QRS complex.	Repeat if clinically indicated.
8. LVEF	LVEF measured by MUGA or ECHO.	Repeat if clinically indicated.
9. Radiological tumor assessment	Contrast enhanced helical CT-scan or MRI, as clinically indicated.	
Every two cycles from the onset of the study treatment until Cycle 6 and every three cycles thereafter.*
 
Patients showing a response must have a confirmatory assessment at least four weeks later.

10. Adverse events	As per NCI-CTCAE v.4.	Throughout the "on treatment" period.**

*A 3-day window will be allowed for laboratory procedures and ECG, a 1-week window for radiological tumor assessments (helical CT-scan or MRI) and LVEF assessments and a 1-day window for clinical assessments (ECOG PS, physical examination, vital signs, weight, BSA).

** "On treatment period" = from first PM01183 infusion to EOT [30 days after the day of the last PM01183 infusion, unless the patient starts a new antitumor therapy or dies (whichever occurs first), in which case the date of administration of this new therapy or the date of death will be considered the date of EOT].

AAGP, alpha-1 acid glycoprotein; AE, adverse event; ALT, alanine aminotransferase; AP, alkaline phosphatase;

	ASSESSMENT	TIME
--	------------	------

AST, aspartate aminotransferase; β -hCG, beta subunit of human chorionic gonadotropin; BSA, body surface area; CPK, creatine phosphokinase; CT, computed tomography; ECG, electrocardiogram; ECHO, echocardiography; ECOG, Eastern Cooperative Oncology Group; EOT, end of treatment; GGT, gamma-glutamyltransferase; INR, international normalized ratio; LDH, lactate dehydrogenase; LVEF, left ventricular ejection fraction; MRI, magnetic resonance imaging; MUGA, multiple-gated acquisition scan; NCI-CTCAE, National Cancer Institute Common Terminology Criteria for Adverse Events; PK, pharmacokinetic; PS, performance status; PT, pro-thrombin time; PTT, partial thromboplastin time; ULN, upper limit of normal; WBC, white blood cells.

5.8 EVALUATIONS AT END OF TREATMENT

The *end-of-treatment visit* will be scheduled within 30 days (\pm 7 days) after the last PM01183 infusion, unless the patient starts a subsequent antitumor therapy, in which case the end-of-treatment visit should be performed immediately before the start of the new therapy (ideally the day before or the same day).

Patients, regardless of the reason for ending the treatment, will have to undergo at the end of treatment the following assessments:

- Complete physical examination.
- ECOG PS.
- Vital signs.
- Concomitant therapies.
- Laboratory tests (coagulation panel, hematology and biochemistry A and B).
- Pregnancy test, ECG or LVEF assessment (if clinically indicated).
- Radiological tumor assessment (the evaluation should be repeated at EOT visit, if not previously done, and if the reason for treatment discontinuation is other than PD).
- Adverse events.

These evaluations will only have to be repeated for those parameters for which no measurement is available within 10 days before the EOT visit, or for those parameters with values that were out of range in the last assessment (grade \geq 2 according to the NCI-CTCAE v.4).

Adverse events must be reported for 30 days after the last study treatment administration. All serious adverse events (SAEs) occurring within 30 days of the last study treatment administration or until the start of a new antitumor therapy, whichever occurs first, will be reported. Beyond this period of time, only those suspected to be treatment-related SAEs will be reported (Section [7.7.2](#)).

The Sponsor will evaluate all safety information that is spontaneously reported by an Investigator beyond the time frame specified in the protocol.

5.9 FOLLOW-UP AFTER END-OF-TREATMENT VISIT

The date and reason of the study discontinuation will be recorded on the patient's CRF (see Section [5.2.1.1](#)).

Only patients who discontinue treatment without PD will have radiological evaluations during follow-up period. The assessments will be performed every two months during the first six months and every three months thereafter until PD, start of a new antitumor therapy, death, or until the end of study date (clinical cutoff). After PD is documented or

a new antitumor therapy is started, each cohort (except SCLC) will be followed-up at least every six months and up to 12 months after the last patient enrolled received the first PM01183 infusion (a documented phone contact will be acceptable). Patients in the SCLC cohort, after PD, will be followed-up every six months for at least 18 months after the last patient enrolled received the first PM01183 infusion (a documented phone contact will be acceptable).

The end-of-study date (clinical cutoff for each cohort except SCLC) is defined as the time point when all evaluable patients within each cohort have at least 12 months of follow-up from the first PM01183 infusion. Patients with SCLC will be followed-up for at least 18 months after the last patient enrolled received the first PM01183 infusion.

Patients who have withdrawn from the study treatment with an ongoing drug-related AE should be followed every four weeks until event recovery to at least grade 1 or stabilization or until onset of a new antitumor therapy.

Additional parameters and/or increased frequency of observations should be performed at the Investigator's discretion and according to the nature of the observed AEs. In case of death, autopsy data should be provided when available.

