7. STUDY EVALUATIONS

7.1 EFFICACY

The primary objective of this study is to assess the antitumor activity of PM01183 in terms of **overall response rate (ORR)**, primary endpoint, supported by the secondary endpoint duration of response (DR), both assessed by the IA.

ORR will be assessed using the RECIST v.1.1 (see [APPENDIX 4](#)) on a set of measurable lesions identified at baseline as target lesions or as non-target lesions (if any), and followed until disease progression (PD) by an appropriate method (e.g., helical CT-scan, MRI).

Radiological tumor assessment will be performed at baseline, and every two cycles from the onset of the study treatment until Cycle 6 or evidence of PD. After Cycle 6, tumor assessment will be performed every three cycles until evidence of PD. If an objective response is observed, according to the RECIST v1.1, it must be confirmed by the same method at least four weeks after the date of the first documentation of response.

ORR is defined as the percentage of evaluable patients with a confirmed response, either complete (CR) or partial response (PR), from the start of treatment to the date of progression or the start of a subsequent therapy or end of patient's follow-up, according to the RECIST (v. 1.1).

DR will be calculated from the date of first documentation of response to the date of first documented PD, recurrence or death due to any cause in the responder patients.

The date of response, the date of radiological or clinical PD, according to the investigator assessment and the independent assessment by IRC when applicable (i.e., SCLC cohort), and the date of death will be registered and documented, as appropriate.

A copy of CT-scans or MRIs can be requested by the Sponsor in selected cases.

In SCLC patients, anonymized copies of all the images obtained throughout the study must be submitted to the Sponsor. These copies of CT scans, MRIs and any other documented methods to evaluate tumor response or progression in the SCLC cohort should be available for external radiological review by an IRC. The IRC will determine the patient's best response and assign the date of first documentation of response and progression/censoring according to RECIST v.1.1.

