3.3 Endpoints

The following are the endpoints defined in the protocol. See further detail in the efficacy section.

Primary Endpoint:

- Overall Response Rate (ORR) in each tumor type. ORR is defined as the percentage of patients with a confirmed response, either complete (CR) or partial (PR), according to the RECIST (v.1.1).

Secondary Endpoints:

Efficacy (all cohorts):

- Duration of Response (DR) by IA, defined as the time between the date when the response criteria (PR or CR, whichever one is first reached) are fulfilled to the first date when PD, recurrence or death is documented.
- Clinical Benefit by IA, defined as response or stable disease lasting over four months ($SD \geq 4$ months).
- Progression-free Survival (PFS) by IA, defined as the period of time from the date of first infusion to the date of PD, death (of any cause), or last tumor evaluation.
- PFS4/PFS6 by IA, defined as the Kaplan-Meier estimates of the probability of being free from progression and death after the first infusion at these time points (4 and 6 months).
- OS, defined as the period of time from the date of first infusion to the date of death or last contact in case of patients lost to follow-up or alive at the clinical cut-off established for the cohort.
- OS6/OS12, defined as the Kaplan-Meier estimates of the probability of being alive after the first infusion at these time points (6 and 12 months).

Efficacy (only in the SCLC cohort):

- ORR, Clinical Benefit, DR, PFS and PFS4/PFS6 by IRC. The same definitions detailed for IA but following IRC evaluation will be used.

Plasma Pharmacokinetics (PK) of PM01183

- Non-compartmental (NCA) PK parameters: area under the curve (AUC), maximum plasma concentration (C_{max}), clearance (CL) and half-life ($t_{1/2}$). Population PK parameters of the compartment model to be developed (initially based on Volumes and Clearance), and PK/PD correlation parameters, if applicable.

Pharmacogenetics:

- This analysis will be performed in those patients who signed the written informed consent (IC) for the pharmacogenetic sub-study. The presence or absence of known polymorphisms from a

single sample collected at any time during the study, but preferably just before treatment start in Cycle 1, will be assessed to explain the individual variability in the main PK parameters.

Pharmacogenomics (PGx):

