Progression-free survival (PFS) is defined as the time from the date of start of treatment to the date of documented progressive disease (PD) by RECIST v1.1 or death (regardless of the cause of death), whichever comes first. Patients who progress or die will be considered to have had an event of progression, except if this event occurs after the start of subsequent antitumor therapy, in which case the patient will be censored at the time of last disease assessment prior to or on the first day of the first subsequent antitumor therapy. If the patient is lost for the assessment of progression during the follow-up period, or has more than one missing follow-up between the date of last tumor assessment and the date of progression, death or further antitumor therapy, the PFS/DR will be censored at the date of last valid disease assessment before the missing evaluations.

The date of response, the date of radiological progression, according to the investigator assessment and the independent assessment by IRC when applicable (i.e., SCLC cohort), the date of clinical PD and the date of death will be registered and documented, as appropriate.

Overall survival (OS) is defined as the time from the date of start of treatment to the date of death or last contact. **One year (1y-OS)/6 months overall survival** is defined as the Kaplan-Meier estimate of the probability of patients being alive at 12/6 months after the date of start of treatment.

A sensitivity analysis for all cohorts but SCLC will be performed for ORR, Clinical Benefit Rate, PFS and OS in the “All Treated Patients population”. For the SCLC cohort, the sensitivity analysis will be carried out the “All Evaluable Patients”.

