(*) Confirmed CR + PR. Binomial exact estimator and 95% CI.

Table 11.3.3.30 DR by IA and IRC excluding CTFI < 30.

	IA	IRC
N		
Events		
Censored		

Median DR		
DR at 4 months		
DR at 6 months		
DR at 12 months		

Kaplan-Meier plot will also be shown (Figure 11.3.3.30.1 DR by IA excluding CTFI<30 (All treated patients), Figure 11.3.3.30.2 DR by IRC excluding CTFI<30 (All treated patients) and 11.3.3.30.3 DR by IA and IRC excluding CTFI<30 (All treated patients))

Table 11.3.3.31 Clinical benefit rate and Disease control rate by IA and IRC excluding CTFI<30 (All treated patients).

		Percentage	Lower 95% limit	Upper 95% limit
IA	Clinical benefit rate*			
	Disease control rate**			
IRC	Clinical benefit rate*			
	Disease control rate**			

(*) CR + PR + SD \geq 4 months. Binomial exact estimator and 95% CI.

(**) CR + PR + SD. Binomial exact estimator and 95% CI.

Table 11.3.3.32 PFS IA and IRC excluding CTFI<30 (All treated patients).

	IA	IRC
N		
Events		
Censored		
Median PFS		
PFS at 4 months		
PFS at 6 months		
PFS at 12 months		

Kaplan-Meier plot will also be shown (Figure 11.3.3.32.1 PFS by IA excluding CTFI<30 (All treated patients), Figure 11.3.3.32.2 PFS by IRC excluding CTFI<30 (All treated patients) and Figure 11.3.3.32.3 PFS by IA and IRC excluding CTFI<30 (All treated patients))

Table 11.3.3.33 OS excluding CTFI<30 (All treated patients).

	OS
N	
Events	
Censored	
Median OS	
OS at 6 months	
OS at 12 months	
OS at 24 months	

Kaplan-Meier plot will also be shown (Figure 11.3.3.33).

DR and PFS considering event in the clinical progressions:

Table 11.3.3.34 DR IA giving event in clinical PD (All treated patients).

	DR
N	
Events	
Censored	
Median DR	
DR at 4 months	
DR at 6 months	
DR at 12 months	

Kaplan-Meier plot will also be shown (Figure 11.3.3.34).

Table 11.3.3.35 PFS IA giving event in clinical PD (All treated patients).

	PFS
N	
Events	
Censored	
Median PFS	
PFS at 4 months	
PFS at 6 months	
PFS at 12 months	

Kaplan-Meier plot will also be shown (Figure 11.3.3.35).

Survival in responders:

Table 11.3.3.36 OS in responders by IA and by CTFI (All treated patients).

	CTFI < 90 days*			CTFI ≥ 90 days*			Total***
	R**	RR**	Total*	S**	VS**	Total*	
N							
Events							
Censored							
Median OS							
OS at 6 months							
OS at 12 months							
OS at 24 months							

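### SCLC cohort: scans stop at PD without IRC confirmation, so IRC PFS and DR may be biased upward, and no IRC-based sensitivity analysis tests this

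*Protocol*

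**What the plan says.** **Imaging.** Protocol 7.1 schedules scans every two cycles to Cycle 6. "After Cycle 6, tumor assessment will be performed every three cycles until evidence of PD". Protocol 5.8 repeats the scan at the end-of-treatment visit only "if not previously done, and if the reason for treatment discontinuation is other than PD". Protocol 5.9 then limits later imaging: "Only patients who discontinue treatment without PD will have radiological evaluations during follow-up period". After PD, SCLC patients are contacted every six months, and a phone call is enough. None of these sections says whose PD ends imaging, and none asks for an IRC reading before treatment or scanning stops. Copies of the SCLC images "should be available for external radiological review by an IRC" (Protocol 7.1).

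**Endpoints.** For the IRC endpoints, SAP 3.3 says: "The same definitions detailed for IA but following IRC evaluation will be used". Under SAP 6.1, "Patients who progress or die will be considered to have had an event of progression, except if this event occurs after the start of subsequent" (meaning new anticancer treatment). Censoring then falls at the last assessment up to that start. PFS and DR are also censored at the last valid assessment when more than one follow-up is missing before the event.

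**Sensitivity analysis.** SAP 8.11 and 11.3 list, under wording that covers both investigator assessment (IA) and IRC, an analysis counting clinical progressions without images as events. The only shells for it, Table 11.3.3.34 (DR) and "Table 11.3.3.35 PFS IA giving event in clinical PD (All treated patients"), are for IA.

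**The concern.** A patient whom the investigator judges to be progressing is probably at higher risk than one still on schedule. If the IRC sees no PD on that scan and imaging then ends, the IRC record stops just as risk may be rising. Kaplan-Meier estimation assumes that censored patients carry the same future risk as those still followed. If they do not, the IRC curve sits too high.

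This matters because the trial is open-label and each cohort has a single arm. The IRC reading is the only independent check on PFS and DR, and the SAP plans to compare it with IA. Without an analysis that counts the disputed patients as events, a reader of the IRC curve cannot tell how much of it rests on their censoring.

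**Working it through.** **Step 1. Follow one patient.** The investigator calls RECIST PD at a scan and the IRC does not.

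- Treatment ends for PD, so there is no further scheduled scan (Protocol 5.8, 5.9, 7.1).
- IRC PFS needs IRC-documented PD or death. IRC PD can no longer be seen on schedule.
- Later events are excluded if new therapy has started or more than one follow-up is missing (SAP 6.1). Death before new therapy, without that gap, is still an event.

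**Step 2. What the planned outputs do with such patients.**

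| Output | Investigator radiological PD, not confirmed by IRC | Clinical PD without images |
|---|---|---|
| Tables 11.3.3.9 (DR), 11.3.3.11 (PFS), IA column | event | not an event in itself |
| Same tables, IRC column | not an event in itself | not an event in itself |
| Tables 11.3.3.34 and 11.3.3.35 | event (IA only) | event (IA only) |
| Listing 11.3.3.15, Table 11.3.3.17, concordance (SAP 6.2) | described | described |

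No IRC analysis has an event in either column.

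**Step 3. Possible size.** The documents give no IRC PFS or DR figure, discordance rate or power for PFS, so there is no stated figure to reproduce. Inputs for an illustration:

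- Median PFS m = 3.5 months, exponential: the topotecan figure in Protocol 1.1, used only for scale.
- Scans every 6 weeks to week 18, then every 9 weeks (Protocol 7.1, three-week cycles). Six weeks is 6 × 12/52.18 = 1.38 months.
- q, the share of investigator PDs not confirmed by the IRC: 10, 20 or 30% (assumed).
- r, the median time from unconfirmed PD to IRC PD or death: 0.5, 1.0 or 2.0 months, or m/(1−q), which gives the same risk as other patients (assumed).

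*Continuous time, every disputed patient censored.* The reported IRC median is m/(1−q): 3.5/0.9 = 3.9, 3.5/0.8 = 4.4 and 3.5/0.7 = 5.0 months. These measure the distance from the investigator's curve. They are not the bias, because they take the investigator's date as the truth. Had scans continued, the median at r = 0.5 would be 3.58, 3.66 and 3.74 months, so the ratios are 1.09, 1.19 and 1.34. At r = m/(1−q) the ratio is 1.00.

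*Protocol scan schedule.* The last scan before 6 months is the third, at week 18. Per interval, S = 2^(−1.38/3.5) = 0.761 and h = 1 − S = 0.239. Let g = 2^(−1.38/r).

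- Reported IRC PFS6 = [1 − (1−q)h]³
- IRC PFS6 with continued scanning = S³ + qh(S² + Sg + g²)
- IA PFS6 = S³ = 44.1%

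| q | Reported | Continued, r = 0.5 | r = 1.0 | r = 2.0 | r = m/(1−q) |
|---|---|---|---|---|---|
| 10% | 48.3% | 45.8% | 46.5% | 47.5% | 48.3% |
| 20% | 52.9% | 47.5% | 48.9% | 50.9% | 52.8% |
| 30% | 57.7% | 49.2% | 51.4% | 54.3% | 57.6% |

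At r = 1.0 the reported figure is about 2, 4 and 6 points high. The excess is about 1, 2 and 3 points at r = 2.0, essentially zero at equal risk, and about 3, 5 and 9 points at r = 0.5.

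*Simulation on the same schedule (40,000 patients, r = 1.0).* It gives excesses of 1.8, 3.9 and 6.3 points. If 40% of disputed patients still count as IRC events, they fall to 1.0, 2.3 and 3.5. At q = 10%, letting the IRC call PD one scan early in 20% of patients lowers reported IRC PFS6 from 48.1% to 45.4%, close to IA at 44.0%. The continued-scanning value is then 43.5%. Early calls therefore pull the IRC curve down and can mask the effect in an IA-versus-IRC comparison.

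No figure was computed for DR. The same reasoning applies to IRC responders.

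**The case against.** The strongest reply is that much of this is already visible. IA PFS and DR count investigator RECIST PD as events and stand beside the IRC results. Concordance, censoring reasons and patient-level IA and IRC times are also planned. A reader might infer from the IA-only shells that no planned analysis counts these patients as events. The documents do not support that: the gap is in IRC-based analyses only.

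A reader might also infer that IRC PFS is overstated. That is not shown either. With equal residual risk there is no bias, deaths before new therapy can count, and the IRC may call PD earlier. The documents do not say that new therapy usually follows PD, and Protocol 1.1 notes that no third-line regimen is approved. The IRC derivation also draws on clinical database information under a charter that is not among the documents (SAP 2), so its handling of investigator PD cannot be settled here.

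Finally, the added analysis might seem redundant, since it equals IA PFS if the IRC never calls PD earlier and clinical PD adds nothing. It also gives the investigator's reading the deciding role for the disputed patients. That is why it belongs beside the main IRC analysis and not in its place. It is not a copy of IA PFS, because it keeps earlier IRC progressions.

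What stands is the mechanism, the missing IRC analysis, and the mismatch between SAP 8.11 and 11.3 and the shells.

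**Conclusion.** IRC PFS and DR in the SCLC cohort are open to informative censoring, and the bias is upward if disputed patients are at higher risk than others. Its size cannot be read from the documents. With 10 to 30% discordance and a 3.5-month median, the illustration gives roughly 0 to 6 points on PFS6 when the median residual time is 1.0 month or longer, and about 9 points at 0.5 months with 30% discordance. Discordance, residual time and the exponential shape are all assumptions.

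The consequence is limited. IRC PFS and DR are secondary, descriptive and carry no decision rule. The primary analysis, ORR by investigator, is unaffected. The point is a cheap improvement to the only independent check on PFS and DR.

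**What to change.** - Keep the main IRC analysis as planned.
- Add IRC versions of Tables 11.3.3.34 and 11.3.3.35 as a sensitivity analysis. The event is the earliest of IRC PD, investigator radiological PD, investigator clinical PD, or death. Show the median and, for PFS, PFS4 and PFS6 beside the main IRC result.
- Label it as a lower bound on IRC PFS and DR, because it treats every unconfirmed investigator PD as a true event on the investigator's date. State in the footnote how the new-therapy and missed-assessment rules of SAP 6.1 apply.
- Align SAP 8.11 and 11.3, which cover IA and IRC, with the shells. Name unconfirmed radiological PD separately from clinical PD without images.

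The cost is two tables and a text edit. Protocol 7.1 and SAP 6.1 already have the radiological and clinical PD dates and the death date recorded, so no scans or visits change. The IRC figures in this analysis will probably look less favourable than the main ones.
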